IST	internal safety team
LLOQ	lower limit of quantification
MAAE	medically attended adverse event
max	maximum
MedDRA	Medical Dictionary for Regulatory Activities
min	minimum
MN	microneutralization
mRNA	messenger ribonucleic acid
NH	Northern Hemisphere

Abbreviation	Definition
NP	nasopharyngeal
PP	per-protocol
PT	preferred term
RT-PCR	reverse transcriptase polymerase chain reaction
SAE	serious adverse event
SAP	statistical analysis plan
SAS	Statistical Analysis System
SD	standard deviation
SoE	schedule of events
SOC	system organ class
TEAE	treatment-emergent adverse event
ULOQ	upper limit of quantification
WHO	World Health Organization
WHODrug Global	World Health Organization drug dictionary

1 Introduction

This statistical analysis plan (SAP), which describes the planned analyses for Study mRNA-1010-P101, is based on the most recent approved clinical study protocol (CSP), Amendment 4, dated 03-Feb-2022, and the most recent approved electronic case report form (eCRF), dated 01-Mar-2022.

In addition to the information presented in the statistical analysis plan section of the protocol (Section 9), which provides the principal features of analyses for this study, this SAP provides statistical analysis details/data derivations. It also documents modifications or additions to the analysis plan that are not “principal” in nature and result from information that was not available at the time of protocol finalization.

Study mRNA-1010-P101 is a Phase 1/2, randomized, stratified, observer-blind, dose-ranging study to evaluate the safety, reactogenicity, and immunogenicity of messenger ribonucleic acid (mRNA)-1010 seasonal influenza vaccine in healthy adults 18 years and older. Study design and analyses for Phase 1/2, and Phase 2 Northern Hemisphere, and Phase 2 Extension parts of the study will be described separately in the SAP, unless otherwise specified.

PPD Biostatistics and Programming team, designee of Moderna Biostatistics and Programming department, will perform the statistical analysis of the safety, reactogenicity, and immunogenicity data; Statistical Analysis System (SAS) Version 9.4 or higher will be used to generate all statistical outputs (tables, figures, listings, and datasets). The SAP will be finalized and approved prior to the primary analysis clinical database lock and treatment unblinding for the study. If the methods in this SAP differ from the methods described in the protocol, the SAP will prevail.

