5.3 Per-protocol (PP) Set

The PP Set consists of all participants in the FAS who comply with the injection schedule, comply with the timing of immunogenicity blood sampling (see definition of criterion below), do not have influenza infection at baseline through Day 29 (as documented by RT-PCR testing), and have no major protocol deviations that impact the immune response. The PP Set will be used as the primary analysis set for analyses of immunogenicity unless otherwise specified. Participants will be analyzed according to the vaccination group to which they were randomized.

Subjects that comply with the timing of immunogenicity blood sampling are required to have a baseline assessment, have at least one post-injection assessment, and have a Day 29 assessment that is within 22 days to 36 days after injection (+7 or -7 days of Day 29).

Subjects with dosing error will be considered as having a protocol deviation. However, the determination of whether to include/exclude subjects from the PP Set due to dosing error will be based on the dosage difference (in μ g) between the actual dose received and the randomized dose. The PP Set exclusion criteria for subjects with dosing error are described in [Table 2](#). For Phase 2 NH and Phase 2 Extension, subjects that are randomized to the

active comparator arm but received less than 40 µg (<40 µg) of the active comparator or any amount of mRNA-1010 will be excluded from the PP Set.

Table 2 PP Set Exclusion Criteria for Dosing Errors

		Randomized Dose				
		Actual Dose Received	50 µg	100 µg	200 µg	Placebo (0 µg)
Phase 1/2	50 µg			Y	Y	Y
	100 µg		Y		Y	Y
	200 µg		Y	Y		Y
	> 0 - 25 µg		Y	Y	Y	Y
	> 25 - 50 µg			Y	Y	Y
	> 50- 75 µg			Y	Y	Y
	> 75 - 100 µg		Y		Y	Y
	> 100 - 125 µg		Y		Y	Y
	> 125 -150 µg		Y	Y	Y	Y
	> 150 – 175 µg		Y	Y	Y	Y
	> 175 -200 µg		Y	Y		Y
	> 200 -225 µg		Y	Y		Y
	> 225 µg		Y	Y	Y	Y
	Placebo (0 µg)		Y	Y	Y	
Phase 2 NH		Randomized Dose				
	Actual Dose Received	25 µg	50 µg	100 µg	Active Comparator ¹	
	25 µg		Y	Y	Y	
	50 µg		Y	Y	Y	
	100 µg		Y		Y	
	> 0 - 25 µg		Y	Y	Y	
	> 25 - 37.5 µg		Y	Y	Y	
	> 37.5 - 50 µg			Y	Y	
	> 50- 75 µg		Y		Y	
	> 75 - 100 µg		Y		Y	
	> 100 - 125 µg		Y		Y	
	> 125 µg		Y	Y	Y	
Phase 2 Extension	Active Comparator ¹	Y	Y	Y		
		Randomized Dose				
	Actual Dose Received	6.25 µg	12.5 µg	25 µg	Active Comparator ¹	
	6.25 µg		Y	Y	Y	
	12.5 µg	Y		Y	Y	

25 μ g	Y	Y		Y
> 0 – 6.25 μ g		Y	Y	Y
> 6.25 – 9.375 μ g		Y	Y	Y
> 9.375 – 12.5 μ g	Y		Y	Y
> 12.5 – 18.75 μ g	Y		Y	Y
> 18.75 - 25 μ g	Y	Y		Y

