> 25 – 37.5 μ g	Y	Y		Y
> 37.5 μ g	Y	Y	Y	Y
Active Comparator ¹	Y	Y	Y	

Note: Y = Excluded from PP Set.

¹ Subjects who are randomized to receive active comparator should receive at least 40 μ g (\geq 40 μ g) of the active comparator and 0 μ g of mRNA-1010 to be included in the PP Set. Subjects in the active comparator arm that received < 40 μ g or any amount of mRNA-1010 will be excluded from the PP Set.

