6.1 General Considerations

For Phase 1/2, Phase 2 NH, and Phase 2 Extension, the Schedules of Events (SoE) are provided in [Appendix E](#).

General considerations for analyses will be applied to Phase 1/2, Phase 2 NH, and Phase 2 Extension, unless otherwise specified. All analyses will be conducted using SAS Version 9.4 or higher. Statistical outputs (tables, figures, listings, and datasets) will refer study participants as subjects and will use injection of IP and injection interchangeably.

For the summary statistics of all numerical variables unless otherwise specified, the display precision will follow programming standards. Please see [Appendix A](#) for variable display standards.

When count data are presented, the percentage will be suppressed when the count is zero in order to draw attention to the non-zero counts. A row denoted “Missing” will be included in count tabulations where specified on the shells to account for dropouts and missing values. The denominator for all percentages will be the number of participants in that vaccination group within the analysis set of interest, unless otherwise specified.

Continuous variables will be summarized using the following descriptive summary statistics: the number of participants (n), mean, standard deviation (SD), median, minimum (min), and maximum (max).

Categorical variables will be summarized using counts and percentages.

Baseline value is defined as the most recent non-missing measurement (scheduled or unscheduled) collected before injection, unless otherwise specified. For immunogenicity tests and nasopharyngeal (NP) swab tests, the baseline is defined as the most recent non-missing result/measurement (scheduled or unscheduled) collected before or on the date (and time, if available) of injection (Day 1).

Study day relative to injection will be calculated as below:

- Study day prior to injection will be calculated as: date of assessment/event – date of injection.
- Study day on or after the date of injection will be calculated as: date of assessment/event – date of injection + 1.

For calculation regarding antibody levels/titers, antibody values reported as below lower limit of quantification (LLOQ) will be replaced by $0.5 \times \text{LLOQ}$. Values that are greater than the upper limit of quantification (ULOQ) will be converted to the ULOQ. Missing results will not be imputed.

The following **analysis periods for safety analyses** will be used in this study:

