6.2.4 Prior and Concomitant Medications

Prior and concomitant medications and non-study vaccination will be coded using the World Health Organization drug dictionary (WHODrug Global). The summary of concomitant medications will be based on the Safety Set. Categorization of prior, concomitant, and post medications is summarized in [Appendix C](#) Table 5.

The number and percentage of participants using concomitant medications and non-study vaccination during the 7-day follow-up period (i.e., on the day of injection and the 6 subsequent days) and during the 28-day follow-up period after the injection (i.e., on the day of injection and the 27 subsequent days) will be summarized by vaccination groups (as defined in [Section 6.1](#)) as follows:

- Any concomitant medications and non-study vaccination within 7 days post-injection
- Any concomitant medications and non-study vaccination within 28 days post-injection
- Seasonal influenza vaccine within 28 days post-injection
- Antipyretic or analgesic medication within 28 days post-injection

A summary table of concomitant medications and non-study vaccination that continued or newly received on the date of injection through 28 days post-injection will be provided by PT in descending frequency in the Total mRNA-1010 group.

Medications taken to prevent or treat pain or fever will be collected in the electronic diary (eDiary), and summaries will be provided based on the Solicited Safety Set by vaccination group (and then by age group) as defined in [Section 6.1](#), including within 7 days after injection, beyond 7 days after injection, and any time after injection.

Prior, concomitant, post medications, and non-study vaccination will be presented in a listing. Medications taken to prevent or treat pain or fever will also be presented in a listing.

Concomitant procedures will be presented in a listing.

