9.2 Appendix B Analysis Visit Windows for Safety and Immunogenicity Analysis

Safety and Immunogenicity Analysis will be summarized using the following analysis visit window for post injection assessments:

Step 1: If the safety and immunogenicity assessments are collected at scheduled visit, i.e., nominal scheduled visit, the data collected at scheduled visit will be used.

Step 2: If the safety and immunogenicity assessments are not collected at the scheduled visit, assessments collected at unscheduled visit will be used using the analysis visit windows described in [Table 3](#) (Phase 1/2) and [Table 4](#) (Phase 2 NH and Phase 2 Extension) below.

If a participant has multiple assessments within the same analysis visit, the following rule will be used:

- If multiple assessments occur within a given analysis visit, the assessment closest to the target study day will be used.
- If there are 2 or more assessments equal distance to the target study day, the last assessment will be used.

Table 3 Phase 1/2 Visit Windows

Visit	Target Study Day	Visit Window in Study Day
Labs		
Day 8	8	[6, 9]
Immunogenicity		
Day 1	1 (Date of Injection)	1, Pre-vaccination
Day 8	8	[2, 18]

Day 29	29	[19, 105]
Day 181	181	≥ 106

Table 4 Phase 2 NH and Phase 2 Extension Visit Windows

Visit	Target Study Day	Visit Window in Study Day
Immunogenicity		
Day 1	1 (Date of Injection)	1, Pre-vaccination
Day 29	29	[2, 60]
Day 91	91	[61, 136]
Day 181	181	≥ 137

9.3 Appendix C Imputation Rules for Missing Prior/Concomitant Medications and Non-Study Vaccinations

Imputation rules for missing or partial medication start/end dates are defined below:

1. Missing or partial medication start date:

- If only Day is missing, use the first day of the month, unless:
 - The medication end date is after the date of injection or is missing AND the start month and year of the medication coincide with the start month and year of the injection. In this case, use the date of injection.
- If Day and Month are both missing, use the first day of the year, unless:
 - The medication end date is after the date of injection or is missing AND the start year of the medication coincide with the start year of the injection. In this case, use the date of injection
- If Day, Month, and Year are all missing, the date will not be imputed, but the medication will be treated as though it began prior to the injection for purposes of determining if status as prior or concomitant.

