2. Missing or partial medication end date:

- If only Day is missing, use the earliest date of (last day of the month, study completion, discontinuation from the study, or death).
- If Day and Month are both missing, use the earliest date of (last day of the year, study completion, discontinuation from the study, or death).

- If Day, Month, and Year are all missing, the date will not be imputed, but the medication will be flagged as a continuing medication.

In summary, the prior, concomitant, or post categorization of a medication is described in [Table 5](#) below.

Table 5 Prior, Concomitant, and Post Categorization of Medications and Non-Study Vaccinations

Medication Start Date	Medication End Date		
	< Injection Date of IP	≥ Injection Date and ≤ Injection Day + 27 Days After Injection	> 28 Days After Injection [1]
< Injection date of IP [2]	P	P, C	P, C, A
≥ Injection date and ≤ 28 days after injection	-	C	C, A
> 28 days after injection	-	-	A

A = Post; C = Concomitant; P = Prior

[1] includes medications with completely missing end date

[2] includes medications with completely missing start date

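### Do the Day 29 per-protocol window in SAP 5.3 and the open lower dose limit in its Table 2 need to be changed?

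*SAP*

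**What the plan says.** **Window.** SAP 5.3 asks that participants "have a Day 29 assessment that is within 22 days to 36 days after injection (+7 or -7 days of Day 29". SAP 6.1 defines study day: "Study day on or after the date of injection will be calculated as" the date difference plus one, so injection is Study Day 1 and Day 29 falls 28 elapsed days later. The analysis windows in Appendix B, Table 4, are headed "Visit Window in Study Day". The Day 29 visit is allowed from −7 to +3 days in both Phase 2 parts (SAP 9.5.2 and 9.5.3) and ±2 days in Phase 1/2 (SAP 9.5.1).

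**Counting elsewhere in the SAP.** Section 6.2.4 refers to medication use "during the 28-day follow-up period after the injection (i.e., on the day of injection and the 27 subsequent days", which counts the injection day. A column of Appendix C, Table 5, ends at "Injection Day + 27 Days After Injection".

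**Dosing errors.** SAP 5.3 bases PP exclusion on the difference in µg "between the actual dose received and the randomized dose" and gives the detail in Table 2. In the Extension block, the row for received doses above 0 and up to 6.25 µg carries no exclusion mark in the 6.25 µg column. The comparator has its own rule in the table footnote: "Subjects who are randomized to receive active comparator should receive at least 40" µg, out of 60.

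**Precedence.** SAP section 1 states: "If the methods in this SAP differ from the methods described in the protocol, the SAP will prevail".

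**The concern.** One criterion is written in two forms that differ by a day if taken literally. Study Day 22 is an allowed Phase 2 visit day, so a program built on elapsed days would remove participants who kept to the schedule from the primary immunogenicity set. The protocol's PP definition gives no numeric window to settle the matter, and the Day 29 window in Appendix B, Table 4, runs from Study Day 2 to 60, so it does not help either.

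The dosing table looks uneven. As a share of the randomized dose, the PP lower limit is 75% in the Extension 12.5 and 25 µg arms, 67% for the comparator and 50% in the lowest Phase 1/2 arm. The Extension 6.25 µg arm accepts any dose above zero. A badly underdosed participant could stay in that arm's PP Set and pull its geometric mean titer (GMT) down.

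**Working it through.** **Window.** Study day = elapsed days + 1 (SAP 6.1).

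- Bracketed form: 29 − 7 = 22 and 29 + 7 = 36, so Study Days 22 to 36, or 21 to 35 elapsed days. The printed 22 and 36 are reproduced exactly as study days.
- Elapsed reading of the phrase: 22 + 1 = 23 and 36 + 1 = 37, so Study Days 23 to 37.
- Both span 15 days. Only Study Days 22 and 37 change status.
- Phase 2 visits may fall on Study Days 29 − 7 = 22 to 29 + 3 = 32, so Day 22 is the only scheduled day at issue. Phase 1/2 visits (Study Days 27 to 31) are unaffected.

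**Which count the SAP uses.** SAP 6.1 and 6.2.4 both define 28 days as the injection day plus 27. In Table 5 of Appendix C, the column ending at injection day + 27 (Study Day 28) is followed by one for more than 28 days after injection. These columns adjoin only if 28 days after injection means Study Day 28. On an elapsed count, a medication ending on Study Day 29 would fall in neither. With the injection day counted, 22 to 36 days after injection is Study Days 22 to 36, and the two forms agree.

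**Cost of a literal slip.** The documents give no distribution of visit days, so let an assumed share s be sampled on Study Day 22. The loss is s × N and the interval widening is 1/√(1 − s) − 1.

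- s = 1%: 5 of 500 (NH), 2 of 200 (Extension), 0.5% wider.
- s = 5%: 25 of 500, 10 of 200, 2.6% wider.

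**Table 2.** Take a fixed tolerance T in µg around the randomized dose. Where the bands of neighbouring arms overlap, cut at the midpoint of the two doses.

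| Part (T) | Arm | Dose ± T | Midpoint cut | Result | Table 2 |
|---|---|---|---|---|---|
| Phase 1/2 (25) | 50 | 25 to 75 | – | 25 to 75 | 25 to 75 |
| | 100 | 75 to 125 | – | 75 to 125 | 75 to 125 |
| | 200 | 175 to 225 | – | 175 to 225 | 175 to 225 |
| Phase 2 NH (25) | 25 | 0 to 50 | 37.5 above | 0 to 37.5 | 0 to 37.5* |
| | 50 | 25 to 75 | 37.5 below | 37.5 to 75 | 37.5 to 75* |
| | 100 | 75 to 125 | – | 75 to 125 | 75 to 125* |
| Extension (12.5) | 6.25 | −6.25 to 18.75 | 9.375 above | 0 to 9.375 | 0 to 9.375 |
| | 12.5 | 0 to 25 | 9.375 below, 18.75 above | 9.375 to 18.75 | 9.375 to 18.75 |
| | 25 | 12.5 to 37.5 | 18.75 below | 18.75 to 37.5 | 18.75 to 37.5 |

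Lower ends are exclusive. *The NH block is damaged in the text available here. Its limits are read from the row cut-points and the SAP 5.4 group boundaries, and should be checked against the original table.

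In µg, the Extension 25 µg arm accepts a shortfall of just under 25 − 18.75 = 6.25. The largest possible shortfall in the 6.25 µg arm is also just under 6.25. Only the 12.5 µg arm is tighter, at 12.5 − 9.375 = 3.125.

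**Cost of one retained complete non-responder.** GMT fall = 1 − f^(−1/n), for an assumed mean rise of f = 2, 4 or 8.

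- n = 50 (Extension arm): 1.4%, 2.7%, 4.1%.
- n = 150 (NH arm): 0.5%, 0.9%, 1.4%.
- Seroconversion falls by at most 1/50 = 2.0 or 1/150 = 0.7 percentage points.

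For scale, the 95% CI factor for a 50-person GMT, 2^(t × SD/√50), is 1.22 to 1.48 each way for an assumed log2 SD of 1 to 2.

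**The case for a change.** On the window, the strongest argument is that SAP 5.3 is the only source of a numeric limit and a program should not depend on inference. The Table 5 cell taken alone does use an elapsed count, and protocol 8.4.15 counts elapsed days for solicited reactions. So the phrase is loose. But the bracket in the same sentence fixes the meaning, and Study Day 22 is also where the Phase 2 visit window opens. The PP window runs past that visit window, over Study Days 33 to 36, which the SAP is entitled to choose.

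On dose, the open end resembles the Safety Set grouping in SAP 5.4, which assigns people to groups and does not judge adherence. Table 2 also closes the top end in the Extension (above 37.5 µg is excluded) where SAP 5.4 leaves it open. Within the 6.25 µg column an excess above 9.375 − 6.25 = 3.125 µg is excluded, while a shortfall of nearly 6.25 µg is kept. Those observations are correct. They follow from the arm having a neighbouring dose above it and none below. Percentages of the randomized dose are not the SAP's criterion: Phase 1/2 tolerates the same 25 µg shortfall at 50 µg (50%) and at 200 µg (12.5%). What remains is that the SAP does not state its tolerance or say that the blank cell is deliberate.

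**Conclusion.** No change follows. The window is a wording slip with one sensible reading, Study Days 22 to 36, which analysts will program. Even the literal reading would cost only a little precision, under a rule that is the same in every arm and so does not bias the comparison with the active comparator.

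The Table 2 point is not shown to be an error. A lower limit for the lowest Phase 2 arm set by the same µg-difference rule as the other mRNA-1010 arms would fall at 25 − 25 = 0 in NH and 6.25 − 12.5 = −6.25 in the Extension, so the cell would stay blank. A stricter limit would be a preference. Its effect is hypothetical: it needs a gross underdose, although protocol 6.4 has staff confirm that the entire dose was given, and one such case would shift the GMT by much less than its confidence interval.

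This rests on two assumptions: that the fixed-tolerance pattern, inferred from the limits and not stated in the SAP, is the one intended; and that the original NH block reads as taken here.

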5.4 Safety Set

The Safety Set consists of all randomly assigned participants who receive the IP. The Safety Set will be used for analysis of safety except for the solicited ARs. Participants will be included in the vaccination group corresponding to the vaccination they actually received according to the following rules:

For Phase 1/2:

- mRNA-1010 50 μ g group: If the received dose of mRNA-1010 is > 0 μ g and \leq 75 μ g
- mRNA-1010 100 μ g group: If the received dose of mRNA-1010 is > 75 μ g and \leq 150 μ g
- mRNA-1010 200 μ g group: If the received dose of mRNA-1010 is > 150 μ g
- Placebo group: If the received dose of mRNA-1010 is 0 μ g

For Phase 2 NH:

- mRNA-1010 25 μ g group: If the received dose of mRNA-1010 is > 0 μ g and \leq 37.5 μ g
- mRNA-1010 50 μ g group: If the received dose of mRNA-1010 is > 37.5 μ g and \leq 75 μ g
- mRNA-1010 100 μ g group: If the received dose of mRNA-1010 is > 75 μ g

- Active comparator group: If the received dose of active comparator is $\geq 40 \mu\text{g}$ and mRNA-1010 is $0 \mu\text{g}$.

For Phase 2 Extension

- mRNA-1010 6.25 μg group: If the received dose of mRNA-1010 is $> 0 \mu\text{g}$ and $\leq 9.375 \mu\text{g}$
- mRNA-1010 12.5 μg group: If the received dose of mRNA-1010 is $> 9.375 \mu\text{g}$ and $\leq 18.75 \mu\text{g}$
- mRNA-1010 25 μg group: If the received dose of mRNA-1010 is $> 18.75 \mu\text{g}$
- Active comparator group: If the received dose of active comparator is $\geq 40 \mu\text{g}$ and mRNA-1010 is $0 \mu\text{g}$.

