6.3 Safety Analysis

The following description of safety analyses will be applied to Phase 1/2, Phase 2 NH, and Phase 2 Extension, unless otherwise specified.

Safety and reactogenicity will be assessed by clinical review of all relevant parameters including solicited ARs (local and systemic), unsolicited AEs (including any clinical safety laboratory abnormalities for Phase 1/2), treatment-related AEs, severe AEs, SAEs, AESIs, MAAEs, AEs leading to withdrawal from study vaccine and/or study participation, vital signs measurement, and physical examination findings. Solicited ARs and unsolicited AEs will be coded by SOC and PT according to MedDRA. AESIs are defined and described in detail in the protocol. The Toxicity Grading Scale for Healthy Adult and Adolescent

Volunteers Enrolled in Preventative Vaccine Clinical Trials (Department of Health and Human Services [DHHS] 2007) is used in this study for solicited ARs as presented in the protocol.

All safety analyses will be based on the Safety Set, except summaries of solicited ARs, which will be based on the Solicited Safety Set. All safety analyses will be provided by vaccination group (and then by age group) unless otherwise specified.

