6.3.1 Adverse Events

A treatment-emergent AE (TEAE) is defined as any event occurring during the study not before exposure to study vaccine or any event already present that worsens after exposure to study vaccine. Worsening of a pre-existing condition after vaccination will be reported as a new AE.

AEs will also be evaluated by the investigator for the coexistence of MAAE and/or AESI. MAAE is defined as an AE that leads to an unscheduled visit to a healthcare practitioner. AESI is an AE (serious or nonserious) of scientific and medical concern specific to the Sponsor's product or program, for which ongoing monitoring and immediate notification by the Investigator to the Sponsor are required. All AEs will be coded by SOC and PT using MedDRA.

Unsolicited AEs within 28 days after vaccination will be summarized by vaccination group. SAE, AESI, MAAE, and AE leading to discontinuation from the study up to 28 days after vaccination and overall period will be summarized by vaccination group. See [Section 6.1](#) for definitions of analysis groups and analysis period.

All summary tables (except for the overall summary of AEs) for unsolicited TEAEs will be presented by SOC and/or PT with counts of participants included. SOCs will be displayed in internationally agreed order. PTs will be displayed in descending order of frequency of Total mRNA-1010 group and then alphabetically within SOC. When summarizing the number and percentage of participants with an event, participants with multiple occurrences of the same AE or a continuing AE will be counted once. Participants will be presented according to the highest severity in the summaries by severity, if participants reported multiple events under the same SOC and/or PT.

Percentages will be based upon the number of participants in the Safety Set within each vaccination group.

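### In both Phase 2 parts, SAP 5.4 gives no safety group to a participant who received some, but less than 40 µg, of active comparator and no mRNA-1010

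*SAP*

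**What the plan says.** SAP 5.4 sets no minimum dose for membership: "The Safety Set consists of all randomly assigned participants who receive the IP". The licensed comparator is an investigational product in both Phase 2 parts (Protocol 6.1), at a nominal 60 µg in 0.5 mL. SAP 5.4 then places each person in the group "corresponding to the vaccination they actually received according to the following rules".

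The rules for Phase 2 NH and Phase 2 Extension have the same structure. Three bins cover mRNA-1010 doses above 0 µg, and the top bin has no upper limit. The fourth rule, "Active comparator group: If the received dose of active comparator is" at least 40 µg, also requires that mRNA-1010 is 0 µg. No residual category follows. The Phase 1/2 control rule is simpler: "Placebo group: If the received dose of mRNA-1010 is 0" µg.

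The same 40 µg figure appears in SAP 5.3, which removes from the Per-protocol Set anyone randomized to the "active comparator arm but received less than 40" µg. The footnote to SAP Table 2 repeats it: "Subjects in the active comparator arm that received < 40" µg, or any mRNA-1010, are excluded.

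On reporting, SAP 6.3 states: "All safety analyses will be provided by vaccination group (and then by age group) unless otherwise specified". SAP 6.3.1 adds: "Percentages will be based upon the number of participants in the Safety Set within each vaccination group".

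**The concern.** A safety grouping rule should place every member of the Safety Set in exactly one group. Here a floor suited to an immunogenicity set has been carried into a safety rule, and one kind of treated participant is left without a column. The plan foresees this participant, because SAP 5.3 deals with comparator doses below 40 µg, but only for the Per-protocol Set.

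The treatment is also uneven between arms. A partial mRNA-1010 dose of any size above 0 µg is grouped for safety, while a comparator dose below two thirds of nominal is not. Safety and reactogenicity are a primary objective in both Phase 2 parts, and each comparator arm has about 50 participants, so one person is visible in a percentage. If the gap is not closed in advance, someone will have to settle it when the dose received, and possibly the outcome, is already known.

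**Working it through.** The plan gives no figure to reproduce. The check is whether the rules are complete.

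**Inputs.** Let m be the mRNA-1010 dose received and c the comparator dose received, both in µg. The rules in SAP 5.4 are:

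- Phase 2 NH: 0 < m ≤ 37.5; 37.5 < m ≤ 75; m > 75; or c ≥ 40 and m = 0.
- Phase 2 Extension: 0 < m ≤ 9.375; 9.375 < m ≤ 18.75; m > 18.75; or c ≥ 40 and m = 0.
- Phase 1/2: 0 < m ≤ 75; 75 < m ≤ 150; m > 150; or m = 0.

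**Logic.** In each Phase 2 part the three bins together cover all m > 0 without overlap. Among people with m = 0 who received any product (c > 0), only c ≥ 40 is covered. The uncovered region is m = 0 with 0 < c < 40.

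**Enumeration.** The rules were evaluated with m from 0 to 250 in steps of 0.625 and c from 0 to 70 in steps of 0.5, requiring that some product was received.

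| Part | Dose pairs with no group | Where they lie | Pairs with more than one group |
|---|---|---|---|
| Phase 2 NH | 79 | m = 0, c = 0.5 to 39.5 | 0 |
| Phase 2 Extension | 79 | m = 0, c = 0.5 to 39.5 | 0 |

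For Phase 1/2 no dose on the grid is left without a group.

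**Comparison with the Per-protocol rules.** SAP Table 2 excludes Phase 1/2 doses of >0 to 25 µg and of >225 µg whatever the randomized arm, yet SAP 5.4 puts them in the 50 µg and 200 µg safety groups. In the Extension, doses above 37.5 µg are excluded in every column but go to the 25 µg safety group. For mRNA-1010, then, failing the Per-protocol dose limits never costs a person a safety group. For the comparator it does.

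**How large an under-dose is needed.** The floor is 40/60 = 66.7% of nominal. If dose is proportional to volume, 0.5 mL × 40/60 = 0.333 mL, so more than 0.5 − 0.333 = 0.167 mL must be lost.

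**Effect of one case in an arm of 50 (an assumption).** One person is 1/50 = 2.0% of the arm.

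| Situation | Person grouped | Person dropped |
|---|---|---|
| AE in 10 others, not in this person | 10/50 = 20.0% | 10/49 = 20.4% |
| AE in 10, including this person | 10/50 = 20.0% | 9/49 = 18.4% |
| This person has the arm's only SAE | 1/50 = 2.0% | 0/49, percentage suppressed under SAP 6.1 |

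The last row is a bounding case: it needs a rare under-dose and the arm's only SAE in the same person.

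**The case against.** The strongest reply is that the general principle already settles the matter. The lead-in to SAP 5.4, SAP 5.5 and the notes to Protocol Table 14 all group people by what they were given, and someone who received only comparator has one natural group. This is a fair account of what was probably intended. It does not repair the text, because the lead-in makes the listed rules the means of applying the principle, and the comparator rule states a condition that this person fails. Two programmers could code it differently.

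The reply is also right that the event is unlikely. Staff confirm that the whole dose was given (Protocol 6.4), and more than a third of the injection would have to be lost.

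A reader might infer more than the documents support:

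- That safety data would be lost or an SAE hidden. AE and SAE listings (SAP 6.3.1.1) and the dosing-error listing (SAP 6.2.5) still show the person. An SAE not reasonably attributable to another cause triggers a pause and an unscheduled DSMB meeting whatever the group (Protocol 7.1.2).
- That the disposition table would miscount. SAP 6.2.1 builds it on the Randomization Set, as randomized.
- That the solicited reaction tables share the gap. SAP 5.5 groups by the injection received and carries no 40 µg floor.
- That the SAP's precedence over the protocol (SAP 1) compels exclusion. Both documents state the same principle, so that clause adds little.
- That the Phase 1/2 placebo rule alone proves the floor wrong. Saline has no µg dose on which to set one. The mRNA-1010 bins are the better comparison.

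**Conclusion.** The point holds as a gap in a grouping rule. In both Phase 2 parts, SAP 5.4 as written conflicts with its own Safety Set definition for comparator doses above 0 and below 40 µg with no mRNA-1010. This is the only dose region left without a group, and there are no overlaps.

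The consequence is limited to the by-group tables of unsolicited AEs, SAEs, AESIs and MAAEs, and arises only if the rule is applied literally. Each affected person is about 2% of a comparator arm, assuming 50 treated. The documents do not give the number affected, and it is expected to be zero or very few. The plan tests no formal hypotheses (SAP 4.2), and Per-protocol handling of the same case is explicit, so no inference changes. This is a minor correction, worth making because it is specific and nearly free.

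**What to change.** In SAP 5.4, for Phase 2 NH and for Phase 2 Extension, define the active comparator safety group as comparator > 0 µg and mRNA-1010 = 0 µg. Keep the 40 µg floor in SAP 5.3 and Table 2 for the Per-protocol Set only.

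The revised rule covers every recipient with m = 0, so the four rules become exhaustive. They stay mutually exclusive because the bins require m > 0, and nobody already assigned changes group. A cross-reference in SAP 5.5 to the same grouping is optional.

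The cost is one line for each Phase 2 part, with no change to data collection or design. It alters analysis grouping only, not dosing.
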